4.1 Eligibility

Community Intervention Group/Arm

Eligibility to participate in this community intervention will primarily be driven by location of residence and age, since screening CRC have established age criteria for screening initiation. A total of four community health navigators will be deployed in the South Shore community area. Each navigator will be trained to understand the eligibility criteria and determine subject eligibility. For those that consent to take the FIT kit and return it, the navigator will document the participants' eligibility in the appropriate REDCap participant information form (attached).

Standard of Care Comparison Group/Control Arm

Within the Mile Square Health Center system, lay navigators already work to do colorectal cancer screening in the Mile Square Health Center setting. It is standard of care for these navigators to engage patients in health education and awareness regarding the need for colorectal cancer screening. As such, each navigator is familiar with eligibility criteria for screening under standard of care. For the purposes of this study, we will use deidentified aggregate data from the CRC screening navigation program at the Mile Square Health Center in Englewood as a comparison group to evaluate the value of the community intervention relative to standard of care. As general practice, each navigator at MSHC keeps a running tally of the number of patients approached, deemed eligible, and who opt to participate in colorectal cancer screening during each day the navigator works in the health center setting.

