dispensed to participant by the community navigator. The FIT and survey will be returned to the UICC via mail or dropped off at the barber or hair salon using a drop box (to be picked up regularly by research personnel), where it will be processed by key research personnel following the manufacturer's instructions. Participants who receive their FIT from the barber or hair salon will be offered a \$25 gift certificate to the barber or hair salon for use towards a future service. Each community navigator will keep a tally of the number of participants who are approached, eligible, and who decline to participate in screening for evaluation purposes. All potential participants will be informed that declining participation will not influence their ability to participate in any future activities at either business or with the UICC.

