For the standard of care control arm, we will obtain deidentified aggregate data from the Mile Square Englewood patients that are approached following standard practice utilizing clinic schedules, walk-ins, etc. to identify potentially eligible participants for CRC screening during the intervention period. This aggregate data will include the number approached, the number eligible, the number that take and return the FIT kit, and the number of FITs returned. Among those that return the FIT, aggregate data will be provided detailing the proportion of positive FITs, the proportion of positive FIT participants who return for diagnostic services, and the proportion of detected cancers.

Table 2. Subject Enrollment Plan

Screening Target	Community-Based (Intervention Arm)
Colorectal	
 Community navigators will work with local businesses (barber shop, hair salon) to identify and screen eligible community members within or near the South Shore community area. The navigator will engage with each potential participant using the attached script. If the participant is interested, the navigator will document the participant's contact information, and assist the participant in obtaining and returning their FIT. Community navigators will attend community events to post the informational flyer and provide education about CRC to community members. At these events, they will identify and screen eligible community members within or near the South Shore community area. The navigator will engage with each potential participant using the attached script. If the participant is interested, the navigator will document the participant's contact information, and assist the participant in obtaining and returning their FIT.
Screening Target	
 Standard of Care Clinic-Based Comparision Group (Control Arm)

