Colorectal	
 These procedures are a detailed summary of the existing lay navigation program at MSHC. These procedures are unrelated to our research, except to demonstrate how the existing navigation program from which we will obtain deidentified data works. Lay clinic navigator use clinic schedules and walk-ins to identify and screen eligible participants within the Englewood MSHC. The navigator engages with each potential participant using standard scripted language. For interested patients, the navigator documents interest and FIT dispensing as appropriate, and assists the patient in obtaining and returning their FIT. Lay clinic navigators attend community events as normally scheduled to provide community-based health education and referral to the MSHC. At these events, they identify and screen eligible community members within the Englewood community area.

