6.1 Study Design and Procedures

6.2 Dimensions of the RE-AIM framework

The overall aim of this study is to assess the feasibility and efficacy of the community-based CRC screening intervention in increasing CRC screening rates. We have designed this controlled trial in an effort to improve the quality of CRC screening that people receive and to assess whether or not implementing a community-based intervention where FIT tests are dispensed by community stakeholder will increase screening rates for CRC in specific community areas in

Chicago. If we find evidence supporting the efficacy of our intervention, that will demonstrate that community-based CRC screening interventions that actively involve community stakeholders in screening education and implementation may be a potential tool to improve health outcomes among the people that live in medically underserved communities. The RE-AIM framework will be used to evaluate both process and outcomes of the intervention program (Gaglio et al. 2013; Glasgow et al. 1999; Glasgow et al. 2019). The RE-AIM framework has proven utility in assessing program impact. Through the RE-AIM Framework we will be able to assess Reach, Effectiveness, Adoption, Implementation and Maintenance.

Data will be collected to evaluate our ability to “reach” targeted community members, hard to reach community members and the targeted number of participants. This is defined as the absolute number, proportion, and representativeness of individuals who are willing to participate in screening within our target community area. The clinical outcomes proposed through this project include improved screening of high risk populations for CRC screening and improved early detection of cancer through improved screening. To disseminate the findings to key stakeholders and community members, we will hold town hall forums to inform community members of findings from the project and produce infographics that clearly and succinctly communicate study findings.

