6.3 Study Procedures

The expected flow of participants through the study is depicted in Figure 1.

[figure not shown]

Figure 1. Study Design Schematic

Community Intervention Group/Arm

For the intervention arm, community navigators will work with local businesses (barber shops, nail/hair salons, restaurants, etc.) to identify and screen eligible community members within the South Shore community area. In an effort to increase screening among the LGBTQ community, navigators will work with local entertainment venues to post the study flyer in order to provide information to patrons, and identify eligible participants for screening. The navigator will engage with each potential participant using the attached script. If the participant is interested, the navigator will review the study information sheet and ask the participant to provide written consent to participate. Once the participant agrees to participate, the navigator will collect contact information from the participant (see Participant Information Form), and provide the participant with a FIT, a short survey to complete and return with their FIT, and a postage paid envelope addressed for delivery to the UICC. The participant will also have the option to return the FIT at the barber or hair salon using a drop box. If the FIT is not returned within two weeks, the navigator will call the participant to remind them to return the FIT.

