13.1 Regulatory Requirements

13.2 Informed Consent

This research presents no more than minimal risk of harm to the participants. Written informed consent will be obtained by the community navigator prior to dispensing the FIT in the community. During the recruitment process, the community navigator team members will describe the study and screen potentially eligible participants. The community navigator team will use the attached script and informed consent document to inform all potential participants of the study procedures. Interested participants will provide written documentation of consent if they decide to enroll in the study. In addition to training on health education and colorectal cancer screening content, informed consent training for the navigators will include consent simulations in which the trainee will read the consent script and respond to various questions about the purpose and procedures of the project. All navigators will practice explaining the study and obtaining informed consent with the study staff prior to engaging in recruitment and enrollment. All adult participants will provide written informed consent for participation.

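### Only the community arm requires research consent before a kit, and refusing the research is not counted apart from refusing the test, so return per kit and reach may be biased by an unknown amount

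*Combined protocol and SAP*

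**What the plan says.** **Community arm.** Section 13.2 states: "Written informed consent will be obtained by the community navigator prior to dispensing the FIT in the community". Section 6.3 gives the same order for an interested person: "the navigator will review the study information sheet and ask the participant to provide written consent to participate". Contact details, kit and survey come only after that. Section 5.0 repeats this sequence for the barber shop and salon and for community events.

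**Englewood.** Section 4.1 says "we will use deidentified aggregate data from the CRC screening navigation program at the Mile Square Health Center in Englewood as a comparison group". Table 2 in section 5.0 says of the clinic's own procedures: "These procedures are unrelated to our research, except to demonstrate how the existing navigation program from which we will obtain deidentified data works". No research consent step is described for these patients.

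**Counts.** For the community, section 5.0 says: "Each community navigator will keep a tally of the number of participants who are approached, eligible, and who decline to participate in screening", with an equivalent sentence for events. At Englewood, section 4.1 says that each navigator "keeps a running tally of the number of patients approached, deemed eligible, and who opt to participate in colorectal cancer screening". The aggregate data from the clinic are to include "the number approached, the number eligible, the number that take and return the FIT kit, and the number of FITs returned", and section 6.3 adds the number who receive a kit.

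**Outcomes.** Section 6.2 defines reach as the number, share and make-up of "individuals who are willing to participate in screening within our target community area". Section 9.1 (Aim 1) compares FIT return rate and mean return time between South Shore and Englewood. It names kits distributed and kits returned, but does not define the denominator of the return rate and plans nothing for the consent step.

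**The concern.** Consider a person who would do the test but will not sign up for research. In the community that person gets no kit and is outside the kit denominator. At Englewood the same person takes a kit and is inside it. A return rate per kit therefore conditions on a step that only one arm has.

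Reach is defined by willingness to be screened. If this person is entered as declining screening, measured reach falls below what the definition asks for. The tally has no other refusal category, and the wording around it does not separate the two decisions. Section 4.1 treats consent, taking the kit and returning it as one act. Section 5.0 assures people about declining participation without saying whether study or test is meant.

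The comparison of return rates is at stake, and so is the reach figure that is meant to inform later programmes. The missing count cannot be reconstructed once the contacts have taken place.

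**Working it through.** **What can be reproduced.** The only related figure in the plan is the community target of at least 600 (section 5.0). Section 12.1 gives no error rate, power, return rates, effect or control number, so 600 cannot be re-derived. Everything below is illustrative, with no true intervention effect.

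**Notation (all values assumed).** W = share of eligible people willing to test, set at 0.60. c = share of those who also sign consent. rc and rn = return per kit in consenters and in willing non-consenters.

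**Reach.** If consent refusers are entered as declining screening, recorded reach = W × c. For c = 0.9, 0.8, 0.7 and 0.6 this is 0.54, 0.48, 0.42 and 0.36, against a true 0.60. If the tally is read literally, they are not entered as declining and reach need not be understated. They are then part of an unlabelled remainder (eligible minus declined minus enrolled).

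**Return per kit.** With the consent step the rate is rc. Without it, the rate is c × rc + (1 - c) × rn. The artefact is the difference, (1 - c) × (rc - rn), in percentage points:

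| rc, rn | c = 0.9 | c = 0.8 | c = 0.7 | c = 0.6 |
|---|---|---|---|---|
| 0.60, 0.30 | +3 | +6 | +9 | +12 |
| 0.55, 0.35 | +2 | +4 | +6 | +8 |
| 0.50, 0.50 | 0 | 0 | 0 | 0 |
| 0.45, 0.55 | -1 | -2 | -3 | -4 |

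For scale, assume 600 kits in each arm, a 50% control return rate and a two-sided 5% test. A difference of about 8 points then has 80% power. With c = 0.7, rc = 0.55 and rn = 0.35, the rates are 0.55 and 0.49, and the chance of a significant result in favour of the intervention is about 55%.

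**Return per eligible person.** With the consent step this is W × c × rc. Without it, it is W × [c × rc + (1 - c) × rn]. The difference is -W × (1 - c) × rn, which is never positive. In the same scenario:
- with consent: 0.60 × 0.7 × 0.55 = 0.231
- without: 0.60 × (0.385 + 0.105) = 0.294
- difference: -6.3 points, where the per-kit artefact was +6

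**Sensitivity range.** Suppose 600 kits, 330 returned (55%) and 200 consent-only refusals. If those 200 are put back into the denominator:
- none return: 330/800 = 41.25%
- they return at the observed rate: (330 + 110)/800 = 55%, the unadjusted figure again
- all return: (330 + 200)/800 = 66.25%

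**The case against.** A reader might infer that the tally does mix the two refusals, so that reach is understated, and that return per kit favours the intervention. The documents support neither as fact.

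- No rule places consent refusers among those who decline screening. Someone who wants the test but not the study has, read literally, not declined it. The category is undefined, which is less than an established error. The remainder under that reading is no substitute for a count, since the plan does not say it will be derived and it could include other losses.
- No data show that consenters return more kits. The artefact is zero if the rates are equal and negative if they are reversed.
- Section 9.1 leaves the denominator open. Per eligible person, the consent step works against the intervention.
- Kit-takers differ in other ways. Englewood patients are found through clinic schedules and walk-ins. The community arm has a 25-dollar incentive and a reminder call after two weeks, neither of which is described for Englewood. The net bias cannot be signed from consent alone.
- Consent in a prospective arm set against routine aggregate data comes with this design, and section 12.1 states a feasibility purpose. Counting consented participants is also a defensible reading of reach, because section 6.2 mentions reaching the intended number of participants too.

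All of this stands, and it limits the point to a conditional one. It does not remove the difference in selection or supply the missing count.

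**Conclusion.** The concern holds in conditional form. The consent asymmetry and the absence of a count for consent-only refusals are in the text. It follows that kit-takers are selected differently in the two arms and that nothing planned addresses this.

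Return per kit may be biased in either direction, by about -4 to +12 points over the assumed rates. The upper part of that range is as large as the difference that 600 kits per arm could detect. Reach may be understated, but only if consent refusers are recorded as declining screening. All of these sizes rest on assumed values of W, c, rc and rn, and the control number is assumed too.

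A separate count would show the share lost to consent. It would not show how those people would have returned kits, so the result is a range and not a correction.

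**What to change.** 1. **Section 5.0, both community tallies.** Record separately those who decline the FIT and those who would take it but decline research consent. No identifiers are needed. State whether people who decline to the barber or salon partner are counted, since section 5.0 brings in the navigator only once a person is interested.
2. **Section 6.2.** Report reach in two forms, each over eligible people approached: consented, and consented plus consent-only refusals. The second rests on a stated intention to take a kit, which is why both are needed.
3. **Section 9.1.** Define the return rate. Report kits returned per eligible person approached beside kits returned per kit dispensed, in both arms, from counts already planned. Note that the consent step lowers the per-eligible figure in the community arm.
4. **If a sensitivity analysis is added.** Put consent-only refusals back into the community kit denominator over return rates from none to all. The observed rate should not serve as a bound, because it only reproduces the unadjusted result.

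The cost is one extra tally count, a little more analysis, and a range that may be less favourable to the intervention.

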3.0 Objectives/Aims

We propose to address the multiple determinants of health that impact CRC screening in the South Shore community in the UI Cancer Center's catchment area by conducting a quasi-experimental intervention to test the effectiveness of FIT tests dispensed by community stakeholders (community-dispensed) versus FIT tests dispensed using standard of care procedures by a clinic (clinic-dispensed) on FIT test return rates. This

study will follow ACS guidelines for FIT testing, with the South Shore community area assigned to the intervention group (community-dispensed). CRC screening within the Mile Square Englewood Health Center, using standard of care, will serve as our control group to use for comparison (clinic-dispensed). The intervention will include a multifaceted approach to health education and community engagement focused on CRC led by a team of trusted health champions (community leaders, a barber, a hair salon, and community health workers) in the South Shore community area. We specifically propose to investigate the following three specific aims to be achieved over the three-year project period:

Aim 1: To assess the feasibility and efficacy of the community-based CRC screening intervention in increasing CRC screening rates;

Aim 2: To evaluate individual-level knowledge related to CRC screening and risk factors;

Aim 3: To characterize individual -level facilitators and barriers to engaging in CRC screening and related diagnostic tests and treatment when applicable.

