In addition to recruitment efforts in the barber shop and beauty salon, our community navigators who are trained on the study protocol will attend community events in the South Shore and surrounding communities such as the annual African Festival of The Arts (<https://www.aihua.org/african-festival-of-the-arts>) where UICC hosts an informational table each year. These navigators will use the attached CRC screening flyer, and engage with each potential participant to provide information and education about CRC screening using the attached script. If the participant is interested, the navigator will review the study information sheet and ask the participant to provide written consent to participate. Once the participant agrees to participate, the navigator will document the participant's contact information, and assist the participant in obtaining and understanding how to use and return their FIT. The navigator will also give the participant a short survey (attached) to complete. The FIT and survey will be returned to the UICC via mail or dropped off at the barber or hair salon using a drop box, where it will be processed following the manufacturer's instructions. Any positive FIT will be promptly reported (within 48 hours) to the MSHC clinical navigator, who will follow standard practices to register the participant as a patient, and navigate the participant through standard medical care if clinical follow-up is needed due to a positive screening and need for a diagnostic examination within the MSHC System. Participants who receive their FIT from a community navigator outside of the barber or hair salon setting will be offered a \$25 incentive (Walgreens store gift card or cash) to be paid upon receipt of the FIT to UICC. Each navigator will keep a tally of the number of participants who are approached, eligible, and who decline to participate in screening for evaluation purposes.

Standard of Care Comparison Group/Control Arm

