13.3 Subject Confidentiality

As described in section 11.0, no protected health information will be stored with the

electronic datasets, and research datasets will be stored on a secure data server in the UI Cancer Center (maintained by the UIC College of Medicine IT department), accessible only by password, and backed up every night. For the purposes of enrollment and follow-up reminders for return of the FIT, some PHI will be collected, including name and address. This data is collected only because it is necessary to complete the research objectives. This information will be entered into a secure REDCap database. Identifying information for the study participants will be kept separately from the analytic dataset and will only be accessed by the PIs. These precautions are expected to be completely effective in eliminating risks to confidentiality. Identifiers will be kept separate from the study data. At the conclusion of the study, the research data will be stored without any PHI on a secure server in the UI Cancer Center (maintained by the UIC College of Medicine IT department).

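### Section 3.0 and a clause in 6.2 word the test as who dispenses the FIT, but the community arm also has a $25 incentive and a reminder call, so a difference in return rate cannot be credited to dispensing setting

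*Combined protocol and SAP*

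**What the plan says.** The protocol describes the comparison in two ways.

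- **By dispenser.** Section 3.0 sets FITs handed out by community stakeholders against "FIT tests dispensed using standard of care procedures by a clinic (clinic-dispensed) on FIT test return rates". The next two sentences label the arms community-dispensed and clinic-dispensed. Section 6.2 asks whether "implementing a community-based intervention where FIT tests are dispensed by community stakeholder will increase screening rates for CRC".
- **By programme.** Aim 1 in 3.0 reads "To assess the feasibility and efficacy of the community-based CRC screening intervention in increasing CRC screening rates". Section 4.1 (control arm), 9.1 (Aim 1) and 12.1 likewise speak of the community intervention or navigation programme, judged against existing clinic practice. Section 3.0 also says the intervention has several strands, but names only health education and community engagement.

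The community arm has two further components that bear on return:

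- **Incentive (5.0).** Outside the barber shop or salon, participants are offered $25, described as "Walgreens store gift card or cash) to be paid upon receipt of the FIT to UICC". For the businesses themselves, "Participants who receive their FIT from the barber or hair salon will be offered a" $25 gift certificate for a future service. That certificate is not stated to depend on return.
- **Reminder (6.3).** "If the FIT is not returned within two weeks, the navigator will call the participant to remind them to return the FIT". Section 13.3 confirms that reminders are a study procedure: "For the purposes of enrollment and follow-up reminders for return of the FIT, some PHI will be collected".

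For Englewood, Table 2 in 5.0 gives what it presents as a detailed account of the existing navigation programme. It includes help with getting and sending back the kit, but mentions no incentive and no reminder call.

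Section 9.1 compares the FIT return rate and the average return time between the two sites.

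**The concern.** The incentive and the call both act directly on whether a kit comes back, and one form of the incentive is paid only if it does. If the final report follows the wording of 3.0, it will say that community dispensing raised (or did not raise) FIT return. A payment, a phone call, or both could produce the same difference even if dispensing setting had no effect. A health system that then moved dispensing into barber shops without the payment and the call would be relying on a result the study did not produce.

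**Working it through.** The plan states no return rate, return time, effect size or Englewood count, so there is no figure to reproduce. The check sets the sections side by side.

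**1. Components by arm, as described**

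| Component | Community arm | Englewood |
|---|---|---|
| Dispenser | Community navigator or partner business (3.0, 5.0) | Clinic lay navigator (Table 2) |
| Education | Yes (3.0, 5.0) | Yes (4.1) |
| $25, paid on return | Yes, outside barber/salon (5.0) | Not described |
| $25 certificate, no stated dependence on return | Yes, at barber/salon (5.0) | Not described |
| Call if not back in two weeks | Yes (6.3) | Not described; general help with return only |
| Written study consent before the kit | Yes (13.2) | Counts come from ordinary practice (5.0) |

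**2. What the comparison can identify**

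Write the difference in return rate as

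D = dispensing + education differences + incentive + call + site and population.

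The plan observes D only. Every community participant is offered $25 in one form or the other and is subject to the call. No one in that arm receives community dispensing without them. Englewood supplies aggregate counts only, so individual-level adjustment is not possible. The dispensing term cannot be separated from the rest.

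**3. Average return time**

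This is the mean over returned kits. A call that prompts a return which would not otherwise have come, later than the current mean, lengthens it. A call that brings forward a late return shortens it. The direction therefore cannot be predicted.

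**4. Illustration: could the incentive and call alone look like a positive result?**

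The 600 is the minimum enrolment in 5.0. Everything else is assumed: 300 to 1,200 Englewood kits, Englewood return of 30% to 60%, a two-sided 5% test, no dispensing effect, no site difference, and neither component at Englewood. For an incentive-plus-call effect δ,

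power = Φ[(δ − 1.96·SE₀)/SE₁], with SE₀ pooled and SE₁ unpooled.

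Take 600 per arm, 40% against 50%, δ = 0.10:

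- SE₀ = √(2 × 0.45 × 0.55/600) = 0.0287
- SE₁ = √(0.40 × 0.60/600 + 0.50 × 0.50/600) = 0.0286
- power = Φ[(0.10 − 0.0563)/0.0286] = Φ(1.53) ≈ 0.94

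Over the assumed range, the probability of a significant difference is 0.81 to 0.99 for δ = 10 points and 0.29 to 0.57 for δ = 5 points. This shows only that such a result is possible. It does not estimate either effect.

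**5. Precision of a day-14 return proportion**

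Half-width of the 95% interval for the difference = 1.96·√[p(1 − p)(1/600 + 1/n_c)], with p and the Englewood count n_c assumed.

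- p = 20%, n_c = 1,200: 1.96 × √(0.16 × 0.0025) = 3.9 points
- p = 30%, n_c = 600: 1.96 × √(0.21 × 0.00333) = 5.2 points
- p = 40%, n_c = 300: 1.96 × √(0.24 × 0.005) = 6.8 points

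**The case against.** **The plan evaluates a programme and never promises to isolate dispensing.** The 3.0 sentence itself sets community dispensing against a bundle of clinic procedures. The same section describes an intervention with several strands. Section 12.1 gives the primary aim in programme terms, and 9.1 asks only whether rates and times are alike. Section 6.2 draws a hedged conclusion, that "community-based CRC screening interventions that actively involve community stakeholders in screening education and implementation may be a potential tool". Much of this stands: on the programme reading the incentive and the call are legitimate components. But the two framings are left unreconciled, and the only description of the strands in 3.0 leaves out the two components most directly tied to return.

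**Site and population already block attribution.** This also stands. The study is non-randomised, one community against one clinic, with written consent before the kit in one arm only. Dispensing could not be isolated even if incentives and calls were equal. The incentive and the call still need naming, because they are built into one arm by design and act on the outcome itself.

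**A day-14 proportion answers a component question.** It does, which is why it belongs beside the overall rate as a supplement and not in its place.

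Three stronger readings are tempting, and the documents do not support them:

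- *Englewood offers neither incentive nor reminder.* Table 2 is presented as detailed, which makes absence likely. But its mention of help with returning the kit could include reminders, and the community row of the same table omits both components too.
- *The whole $25 incentive depends on return.* Only the payment outside the barber shop or salon is stated to do so.
- *The comparison is worthless.* A programme-level comparison, reported with its limits, fits Aim 1.

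**Conclusion.** The point holds as an attribution problem in the wording of 3.0 and the clause in 6.2, and the plan should be changed. It does not invalidate the trial. A conclusion about dispensing setting would be unsupported. A conclusion about the whole community programme is coherent, but remains non-randomised and confounded with site and population.

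The size of the distortion in return rate or return time cannot be derived from the documents; the power and precision figures above rest on assumed inputs. The conclusion also depends on what Englewood actually does. If it uses similar incentives and reminders, those two components would no longer separate the arms, though the site and population differences would remain.

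**What to change.** 1. In 3.0, 6.2 and the return-rate comparison in 9.1, define the contrast as the whole community programme (dispensing, education, $25 incentive, reminder call) versus Englewood standard of care. State that no conclusion will be drawn about dispensing setting alone, and that the programme difference is non-randomised and confounded with site and population.
2. Ask Englewood whether it uses incentives or reminder calls, and report the answer with the comparison.
3. As a supplementary measure beside the overall return rate, report the proportion of dispensed kits returned by day 14 in both arms, with the same return-date definition. The definition needs care because community kits may come by post or by drop box. Add this count to the Englewood data request: the item lists in 5.0 and in the first control-arm paragraph of 6.3 contain no return times, and only the closing paragraph of 6.3 mentions tracking them. Note with the result that the measure removes the community arm's scheduled call, provided no earlier reminder is made, but not the incentive or the site differences.

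The cost is wording in three sections, one question to Englewood and one extra aggregate count. The downside is a narrower claim.
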